3.10 Subject Enrollment Point

All subjects who are candidates for treatment of in-stent restenosis in coronary arteries will undergo screening for study eligibility and, if applicable, for study enrollment. For any subject enrolled, a signature of informed consent will be obtained. The subject will be considered enrolled into the study upon the completion of all the following:

- A signed subject informed consent.
- Angiographic criteria for enrollment has been met.
- Target lesion is successfully crossed by the guidewire.
- Successful pre-treatment of in-stent restenosis without complication, if applicable.
- CVT Everolimus-coated PTCA Catheter has entered the vasculature.

3.11 Subject Discontinuation

Every subject should remain in the trial until completion of the required follow-up period; however, a subject's participation in any clinical trial is voluntary and the subject has the right to withdraw at any time without penalty or loss of benefit. The reason for withdrawal, when it occurs, must be documented in the subject's medical records. Following study discontinuation, the subject will be followed per the institution's standard of care. Conceivable reasons for discontinuation may include, but are not limited to, the following:

- Subject participation in a clinical trial is voluntary and the subject may discontinue participation (refuse all subsequent testing/follow-up) at any time.
- Investigator may terminate the subject's participation without regard to the subject's consent if the Investigator believes discontinuation in the study is medically necessary.

- Subject does not complete the scheduled follow-up but has not 'officially' withdrawn from the trial (e.g. "lost to follow-up"). This does not apply to missed visits.
- Medical conditions such as the following
 - Reaction to acute treatment requires alternative treatment or intervention (e.g. allergic reaction to everolimus, complication with non-study device) where study objectives cannot be objectively evaluated.
 - Unanticipated hospitalization requiring treatment or therapy conflictive with study objectives and preventing compliance with study requirements.

Site personnel should make all reasonable efforts to locate and communicate with subjects at each contact time point. A minimum of two (2) telephone calls to contact the subject should be recorded in the source documents, including date, time, and initials of site personnel trying to make contact. If these attempts are unsuccessful, a letter should be sent to the subject. If the subject misses two (2) consecutive scheduled contact time points and the above mentioned attempts at communicating with the subject are attempted but unsuccessful, the subject will be considered "lost to follow-up".

A study completion form must be completed when a) the subject is considered "lost to follow- up" (per the above criteria), b) the subject withdraws from the study or c) the investigator withdraws the subject from the study. In each case of subject discontinuation, CVT must be notified of the reason for subject discontinuation. The site will provide this information on the case report form (CRF) and in source documents.

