3. STUDY DESIGN

The CVT-ISR Trial investigates the inhibition of restenosis using the CVT Everolimus-coated PTCA Catheter in the treatment of in-stent stenotic lesions \leq 24 mm in native coronary arteries with reference vessel diameters of 2 to 3.5mm. The clinical study will be a prospective, multicenter, open, single-arm study.

Each subject will be followed for at least 3 years (36 months) after treatment. All subjects will have a follow-up contact or an optional office/hospital/clinic visit at 30 days. A follow-up office/hospital/clinical visit will occur at 6, 12, and a follow up phone call will occur at 24 and 36 months.

To participate in this study, the site will need the resources necessary for conventional vascular surgery as well as for fluoroscopy-guided catheter-based procedures with high quality imaging.

The study participation flow chart is provided in Figure 1.

Figure 1. CVT-ISR Study Participation Flow Chart

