Adjunctive therapies should be avoided if possible. In case of suboptimal procedure results (>50 % residual stenosis, perforation, occlusive complication (recoil) or flow limiting dissection) prolonged balloon inflation should be attempted. If a subject in this study experiences a major dissection or an occlusive complication (as evidenced by decreased target vessel flow, chest pain, or ischemic electrocardiogram (ECG) changes which do not respond to standard rescue techniques), bailout stenting procedures may be performed. All other adjunctive therapies (including but not limited to: laser, atherectomy, cryoplasty or brachytherapy) are not allowed.

If bailout procedures are performed, justification should be documented on the CRF. Subjects undergoing bailout procedures will continue in the study and their data will remain part of the statistical analyses.

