5. ADVERSE EVENTS

5.1 Adverse Events

At each evaluation, the investigator will determine whether any adverse events (AEs) have occurred. For the purpose of this protocol, an adverse event is any untoward medical occurrence, unintended disease or injury, or untoward clinical signs (including laboratory findings) in subjects, users or other person, whether or not related to the investigational medical device.

In this study, subjects should be encouraged to report AEs spontaneously or in response to general, non-directed questioning. If it is determined that an AE has occurred, the investigator should obtain all the information required to complete the AE Form of the CRF.

In addition, subjects will be instructed to contact the investigator, and/or study coordinator if any significant adverse events (e.g., MACE) occur between study evaluation visits.

AE collection will start when CVT Everolimus-coated PTCA Catheter has entered the vasculature.

Adverse events should be followed to resolution or stabilization, and if an ongoing AE changes in severity, a new AE entry for this event should be recorded. If a mild adverse event changes to a moderate or severe adverse event, the end date for the mild event and the start date for the moderate or severe event should be the same. Additionally, the mild event is considered resolved with the initiation of the moderate or severe event.

Adverse events that are present at the end of a subject's participation in the study should be marked as on-going on the case report form and the subject should receive posttreatment follow-up as appropriate.

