6.4 Statistical Analyses

Detailed analyses of the primary endpoints will be performed when all of the subjects complete their primary follow-up visit at 180 days. No effort will be made to impute or extrapolate data to replace missing values. All calculations will be based on available data with missing data excluded.

Analysis of Primary Endpoints

The primary safety endpoint of freedom from target lesion failure (TLF) rate at 6 months post-index procedure will be analyzed using the safety population.

The analysis of the primary effectiveness endpoint of LLL at 6 months will utilize the evaluable populations.

Analysis of Secondary Endpoints

All secondary endpoints will be analyzed using descriptive statistics.

For binary variables, such as technical success counts, percentages and exact 95% confidence intervals using Clopper-Pearson's method will be calculated. For continuous variables, means, standard deviations, and 95% confidence intervals for the mean using the Gaussian approximation will be calculated. If the assumption of normality seems untenable, nonparametric methods will be employed instead.

For time-to-event variables, such as time to target lesion revascularization, survival curves will be constructed using Kaplan-Meier estimates.

Analysis of Other Data

The clinical laboratory values collected will be analyzed by tabulating the number and percentage of subjects with clinically significant changes from baseline for each parameter at each time point.

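### Section 3.11 lets some subjects with a treatment reaction or conflicting hospitalization leave safety follow-up, and section 6.4 then drops those without a recorded TLF from the primary safety rate

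*Combined protocol and SAP*

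**What the plan says.** Section 3.11 (Subject Discontinuation) opens with a retention default: subjects should stay until the required follow-up is complete. It then gives a non-exhaustive list of conceivable reasons for discontinuation. Two are medical:

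- "Reaction to acute treatment requires alternative treatment or intervention (e.g. allergic reaction to everolimus, complication with non-study device"), with the limit "where study objectives cannot be objectively evaluated".
- "Unanticipated hospitalization requiring treatment or therapy conflictive with study objectives and preventing compliance with study requirements".

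On what happens next it says: "Following study discontinuation, the subject will be followed per the institution's standard of care". Beyond that, the section asks for a study completion form and notification of the reason to the sponsor. It specifies no later study contact for safety or vital status.

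Four other sections bear on this:

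- Section 3 (Study Design): "Each subject will be followed for at least 3 years (36 months) after treatment".
- Section 4.3, on bailout: "Subjects undergoing bailout procedures will continue in the study and their data will remain part of the statistical analyses".
- Section 6.2: the safety population is every enrolled subject in whom the procedure was initiated.
- Section 6.4: "All calculations will be based on available data with missing data excluded", with no imputation. No rule says how a subject who leaves before 6 months is counted in the freedom-from-TLF rate.

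**The concern.** The investigational treatment is one procedure at the index visit: a single lesion, up to two catheters, a 60-second inflation. No device treatment remains to be stopped afterwards. Protocol antiplatelet medication continues (section 4.2), but a change of drug does not require leaving follow-up. Discontinuation in section 3.11 therefore means the end of study follow-up and data collection.

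Section 9.6 calls this a first-in-human study, and reactions and complications around the procedure are among the things it most needs to observe to 36 months. If subjects leave because of such an event, and those who leave are at higher risk of TLF than those who stay, deleting their missing outcomes raises the freedom-from-TLF rate. Later event rates are exposed in the same way.

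**Working it through.** **1. Do the sections fit together?** A subject with a procedural complication that needs another intervention could be handled under section 3.11 (may leave) or under the bailout text of section 4.3 (stays, and is analysed). Nothing says which governs. The limit in the first medical ground is undefined. A reaction or an added intervention may make late lumen loss uninterpretable, but cardiac death, target vessel MI, clinically driven TLR and adverse events remain observable, and safety is a stated study objective.

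**2. Inputs for the primary safety endpoint (section 6.3).** N = 50; performance criterion 65%; success if the lower limit of the 90% CI exceeds 65%; worked example of 8 TLFs in 50.

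**3. Formula.** For x event-free subjects of n, the exact (Clopper-Pearson) two-sided 90% lower limit is the 5th percentile of Beta(x, n − x + 1). The upper limit is the 95th percentile of Beta(x + 1, n − x).

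**4. The plan's own figure.** 42/50 = 84.0%, 90% CI 73.0% to 91.8%. This matches the stated 73% to 92%, so the exact method is the one to use.

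**5. Effect of losing would-be failures before their TLF is recorded.** The number lost is an assumption in every row.

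| True TLFs in 50 | Lost unrecorded | Analysed | Rate | Lower limit | Rule |
|---|---|---|---|---|---|
| 11 | 0 | 39/50 | 78.0% | 66.2% | pass |
| 12 | 0 | 38/50 | 76.0% | 64.0% | fail |
| 12 | 1 | 38/49 | 77.6% | 65.6% | pass |
| 12 | 2 | 38/48 | 79.2% | 67.2% | pass |
| 13 | 0 | 37/50 | 74.0% | 61.9% | fail |
| 13 | 2 | 37/48 | 77.1% | 64.9% | fail |
| 13 | 3 | 37/47 | 78.7% | 66.6% | pass |
| 8 | 0 | 42/50 | 84.0% | 73.0% | pass |
| 8 | 3 | 42/47 | 89.4% | 78.9% | pass |

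The boundary lies between 11 and 12 events. With 12, one loss is enough to reverse the result; with 13, three are needed. At the plan's expected 8 events, losses inflate the estimate but change no decision.

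**6. Chance of a wrong pass.** Suppose each would-be failure independently has probability q of leaving unrecorded. With F ~ Bin(50, 0.35) failures and M ~ Bin(F, q) losses, the chance that (50 − F)/(50 − M) passes at a true rate of 65% is:

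| q (assumed) | 0 | 0.05 | 0.10 | 0.20 |
|---|---|---|---|---|
| P(pass) | 3.4% | 5.0% | 6.8% | 13.0% |

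The nominal level is 5%, so on these assumptions it is reached at about q = 0.05.

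**7. What the observed data cannot show.** A result of 38/49 with one early leaver is compatible with a true 39/50 (lower limit 66.2%, pass) or 38/50 (64.0%, fail). Reporting 38/50 alongside 38/49 shows the reader that the conclusion hangs on that subject.

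**The case against.** The strongest reply is that section 3.11 is narrower than it first looks. A reader might infer that any everolimus reaction, or any harm from the study balloon, removes a subject. The text does not say that. The list is permissive and sits under a retention default. The first ground is limited to cases where objectives cannot be evaluated, its device example concerns a non-study device, and the hospitalization ground requires both conflicting therapy and inability to comply. All of this stands, and it reduces the number who could leave. It does not close the route, because the limit is left to site judgement and safety outcomes remain evaluable.

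A reader might also see outright contradictions with section 3 and section 5.1. Neither is one. The 36-month statement is the planned duration, and a withdrawal clause is an exception to it. Section 5.1 does say "Adverse events should be followed to resolution or stabilization", but it also provides for events still open when participation ends. Only the mismatch with the bailout text in section 4.3 needs reconciling, and that text already protects subjects with major dissection or occlusive complications who are bailed out.

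On size, bias requires a subject who meets the ground, leaves before 6 months, has no TLF recorded by then and would later have had one. A TLF recorded before leaving still counts, and an allergic reaction is not itself a TLF component. At the plan's assumed 16% TLF rate, exactly 12 events in 50 has probability of about 4.5%. Section 6.1 adds that statistical significance is neither necessary nor sufficient in this feasibility trial. These points lower the urgency. They do not justify ending data collection that is already scheduled.

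**Conclusion.** The point holds in a limited form. Section 3.11 permits, but does not require, ending study follow-up for some treatment reactions and hospitalizations. With section 6.4 excluding missing data, a subject who leaves in this way before 6 months without a recorded TLF disappears from the primary safety rate. The likely direction favours the device, on the assumption that such subjects carry a higher TLF risk than those who remain.

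The number affected is unknown, and every removal count and q value above is an assumption. What can be said firmly is that the rule is fragile at its boundary, where one unrecorded failure turns a fail (64.0%) into a pass (65.6%). It would be wrong to conclude that the primary result will be biased, or that harmed subjects must leave; the documents support neither. This should be fixed, but it is not a fatal flaw.

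**What to change.** **Section 3.11, reconciled with section 4.3.** Separate stopping study-specific procedures (such as repeat angiography, IVUS or OCT) from ending safety follow-up. State that every subject in whom the study catheter entered the vasculature, which is the last step of enrolment in section 3.10, stays in the scheduled safety contacts to 36 months for adverse events, TLF and vital status unless consent is withdrawn. State also that a medical condition is not in itself a reason to end that data collection. Clinical care and judgements of medical necessity stay with the investigator.

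**Section 6.4.** Add a sensitivity analysis of freedom from TLF that counts every subject who leaves before 6 months without a recorded TLF as a failure. Applying it to all reasons for leaving also covers consent withdrawal and loss to follow-up, which the change to section 3.11 cannot prevent.

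**Cost.** Amendment wording, a few retained contacts that are already in the schedule, and possibly a slightly less favourable sensitivity figure. Counting leavers as failures is deliberately pessimistic, so it should be reported beside the primary analysis and not replace it.

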3.12 Early Termination of the Clinical Trial

CVT, the trial Sponsor, reserves the right to discontinue the clinical study at any stage, with suitable written notice to the investigator. The investigator may also discontinue participation in the clinical trial with suitable written notice to CVT.

CVT and the Study Steering Committee will monitor the progression of the study. The study will be suspended or discontinued early if there is an observation of serious adverse reactions presenting an unreasonable risk to the study population.

Notification of suspension or termination will occur no later than five (5) working days after Sponsor makes the determination. In the event of study suspension or termination, the Sponsor will send a report outlining the circumstances to the IRB/EC and all investigators. A suspended or terminated study may not be re-initiated without approval of the reviewing IRB/EC (where applicable).

4. CONDUCT OF THE STUDY

Study conduct as well as detail of pre-procedure, procedural, discharge and follow up activities are presented in this section of the protocol. Refer to **Table 3** for a summary of pre-procedure, procedure, discharge and follow up activities.

4.1 Baseline Assessments

Subject preparation will occur in accordance with standard hospital policy for the care of interventional endovascular subjects. Baseline assessments will be documented in the subject medical record and on the case report form (CRF) as appropriate.

Subject History

Subject history will include but not be limited to the following risk factors and comorbidities: age, height, weight, body mass index (BMI), gender, hypertension, hyperlipidemia, diabetes mellitus, smoking, ischemic heart disease (history of myocardial infarction, angina pectoris, previous percutaneous or surgical coronary revascularization), history of peripheral vascular disease (previous percutaneous or surgical revascularization), deep vein thrombosis, congestive heart failure, renal insufficiency, renal disease, liver disease, cerebrovascular disease (known carotid artery disease, history of minor or major stroke or transient ischemic attack), and chronic obstructive pulmonary disease (COPD).

Medication History

A medication history should be documented which includes chronic concomitant medications and protocol required medications.

Clinical Assessments

A physical examination should be documented. The exam will include heart rate, blood pressure and body temperature.

Laboratory Assessments

A pregnancy test should be administered to all female subjects of childbearing potential within 14 days prior to the procedure.

The following laboratory tests should be obtained for all subjects within 7 days prior to the index procedure.

- Complete Blood Count
- Creatinine
- Absolute Platelet Count
- Coagulation tests as per standard of care of the hospital (e.g., Prothrombin Time (PT) and activated Prothrombin Time (aPTT).

The following laboratory tests should be obtained for all subjects within 72 hours of the index procedure.

- CK and/or CK-MB and cardiac troponin (cTn)
- 12 lead ECG.

4.2 Concomitant Medical Therapy

Antiplatelet medication should be administered according to hospital routine and in line with the applicable guidelines on Percutaneous Coronary Interventions and the Instructions for Use of the device.

All subjects will receive aspirin (a minimum of 75 mg daily, within 24 hours prior to the procedure) and a loading dose of any approved antiplatelet medication within 24 hours

prior to the procedure or immediately post procedure (within 30 minutes of last catheter removal). If the subject already has taken an appropriate dose of anti-platelet medication within 72 hours prior to the procedure, no loading dose is required.

During the index procedure, heparin or bivalirudin may be administered as per hospital standard of care to maintain adequate anticoagulation.

A GP IIb/IIIa receptor blocker may be administered at the Investigator's discretion.

Following the procedure, subjects will receive a minimum of 75 mg of aspirin daily indefinitely and an appropriate dose of any approved anti-platelet medication for a minimum of 6 months in all subjects or longer per the ACC/AHA/SCAI guidelines⁵ and with the Investigator's discretion.

All antiplatelet/anticoagulant medications will be documented on the CRF from 24 hours preprocedure through the 36-month follow-up assessment.

Table 2 summarizes the study required regimen for antiplatelet medication for subjects enrolled in the study prior and during procedure.

Time Point	Medication	Regimen		
Prior to	Heparin or bivalirudin	As needed		
Procedure	Aspirin	A minimum of 75 mg daily (within 24 hours prior to procedure)		
	Clopidogrel/Plavix, Prasugrel/Effient, Ticagrelor/Brilinta,or Ticlopidine/Ticlid or any market approved antiplatelet indicated.	Loading dose within 24 hours prior to procedure or immediately post procedure (within 30 minutes of last catheter removal)		
		No loading dose is required if the subject has taken at least 3 maintenance doses within 72 hours prior to the procedure		
During Procedure	Heparin or bivalirudin	To maintain adequate anticoagulation per hospital standard of care		
	GP IIb/IIIa receptor blocker	Use at Investigator's discretion		
Post-	Aspirin	A minimum of 75 mg daily indefinitely		

Table 2. CVT-ISR Study Required Antiplatelet Medication Regimen

4.3 ISR PTCA Procedure

Procedural Medications

During the procedure, the subjects will receive appropriate anticoagulation and other therapy according to standard hospital practice. The use of any medication for the treatment of vessel spasm, subject agitation or discomfort, hypotension, arrhythmias and hemodynamic changes during the procedure is at the discretion of the investigator.

Treatment Strategy

The treatment strategy for all subjects enrolled in the clinical investigation is as follows:

- Treatment of a single in-stent restenosis lesion in a native coronary artery with up to two (2) CVT Everolimus-coated PTCA Catheters.
- Target lesion must be treated after meeting all the general and angiographic inclusion and exclusion criteria.
- Pre-dilation of target lesion is mandatory.
- Treatment of target lesion measuring ≤ 24 mm in length by visual estimation in vessel of visually estimated diameter ≥ 2.0 mm and ≤ 3.5 mm.
- Recommendation is to select a CVT EVE-PTCA Catheter with a balloon length that allows for coverage of the targeted lesion plus approximately 2 mm additional coverage, by visual estimate, on each side of the lesion while not allowing the balloon length extend beyond the edges of the stent.

PTCA Procedure

Vascular access should be obtained as per site standard of care (depending on lesion location, subject factors or any other factors that would impact the choice of vascular access).

Angiography must be conducted according to the angiographic core laboratory guidelines.

As a next step, a compatible sheath should be inserted and anticoagulation should be administered as per the Investigator's discretion to obtain or maintain appropriate clotting time (reference section 4.2. Concomitant Medical Therapy). In order to identify the anatomical characteristics of the vasculature and to visualize and define the lesion, selective angiography will be performed. Following angiography, the appropriate catheter size(s) will be selected.

Pre-dilatation will be performed on all subjects per the following sequence: after crossing of the target lesion with a guidewire, pre-dilatation is performed with a non-study balloon catheter, making sure that the balloon length is shorter than previously placed stent

length. Note that the use of a non-drug coated standard semi-compliant balloon or cutting/scoring balloon is allowed.

Record an image of the target lesion after pre-dilatation is completed. Ensure to perform an angiography distal to the target lesion. Assess the subject for any angiographic complications after pre-dilatation and confirm the lesion to be treated meets the study angiographic inclusion and exclusion criteria.

Successful pre-dilatation of the target lesion is defined as:

- Residual stenosis of <30% after pre-dilatation (per visual estimate) AND
- No major (>Grade B) flow-limiting dissection.

In case of unsuccessful pre-dilatation of the target lesion planned to be treated with the investigational device, the subject should be considered a screen failure and all lesions should be treated as per standard of care.

Treatment with CVT Everolimus-coated Catheter

It is recommended to select a CVT EVE-PTCA Catheter with a balloon length that allows for coverage of the targeted lesion plus approximately 2 mm additional coverage, by visual estimate, on each side of the lesion while not allowing the balloon length extend beyond the edges of the stent.

The balloon should be inflated for 60 seconds in order to allow for an optimal drug delivery to the surrounding tissue.

Post-Procedure Angiography Subset

A subset of twenty-five (25) subjects will complete post-procedure angiography assessment of the target vessel, as per the angiographic core laboratory guidelines, at 6 months post-procedure.

The 25 subjects undergoing angiographic follow up will represent the first subjects enrolled into the study, with no more than 15 patients undergoing angiographic follow up from a single site.

Note: The end of the procedure is defined as the time after a complete final angiogram has been performed and the last guidewire and catheter have been removed. In case the subject needs to return to the procedure room and a guiding catheter is reinserted for dilatation, this is considered a reintervention. Removal of the sheath(s) may be done at the Investigators discretion.

All catheters, including the CVT Everolimus-coated PTCA Catheter, should be delivered and deployed per their respective Instructions for Use (reference Appendix E for CVT Everolimus-coated PTCA Catheter IFU). All balloon inflations should be captured per the angiographic core laboratory guidelines.

Intravascular Ultrasound Examination (IVUS)

A subset of fifteen (15) subjects will complete an intravascular ultrasound (IVUS) examination at both the index procedure and at 6 months post-procedure, as per the IVUS core lab guidelines.

The 15 subjects undergoing IVUS examination will represent the first patients enrolled

into the study.

Note: The end of the procedure is defined as the time after a complete final angiogram has been performed and the last guidewire and catheter have been removed. In case the subject needs to return to the procedure room and a guiding catheter is reinserted for dilatation, this is considered a reintervention. Removal of the sheath(s) may be done at the Investigators discretion.

All catheters, including the CVT Everolimus-coated PTCA Catheter, should be delivered and deployed per their respective Instructions for Use (reference Appendix E for CVT Everolimus-coated PTCA Catheter IFU). All balloon inflations should be captured per the core laboratory guidelines.

Optical Coherence Tomography (OCT)

A subset of ten (10) subjects will complete optical coherence tomography (OCT) imaging at both the index procedure and at 6 months post-procedure, as per the OCT core lab guidelines.

The 10 subjects undergoing OCT examination will represent the first subjects enrolled into the study undergoing angiographic follow up and not undergoing IVUS examination.

Note: The end of the procedure is defined as the time after a complete final angiogram has been performed and the last guidewire and catheter have been removed. In case the subject needs to return to the procedure room and a guiding catheter is reinserted for dilatation, this is considered a reintervention. Removal of the sheath(s) may be done at the Investigators discretion.

All catheters, including the CVT Everolimus-coated PTCA Catheter, should be delivered and deployed per their respective Instructions for Use (reference Appendix E for CVT Everolimus-coated PTCA Catheter IFU). All balloon inflations should be captured per the angiographic core laboratory guidelines.

Criteria for Bail-Out or Alternative Procedures

Adjunctive therapies should be avoided if possible. In case of suboptimal procedure results (>50 % residual stenosis, perforation, occlusive complication (recoil) or flow limiting dissection) prolonged balloon inflation should be attempted. If a subject in this study experiences a major dissection or an occlusive complication (as evidenced by decreased target vessel flow, chest pain, or ischemic electrocardiogram (ECG) changes which do not respond to standard rescue techniques), bailout stenting procedures may be performed. All other adjunctive therapies (including but not limited to: laser, atherectomy, cryoplasty or brachytherapy) are not allowed.

If bailout procedures are performed, justification should be documented on the CRF. Subjects undergoing bailout procedures will continue in the study and their data will remain part of the statistical analyses.

